#### Version history

Version	Changes
0.1	Initial draft
0.2	Inclusion of formulas for plasma volume and blood volume, Details for regression models Addition of baseline parameters
0.3	Clarification of analyses and time points to be used
1.0	Inclusion of Cystatin C formulas for estimation of GFR

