## 1 Background

### 1.1 Trial objective

This is an investigator-initiated, one-armed phase II clinical trial designed to primarily evaluate the safety and functionality of the FAST PV and measured Glomerular Filtration Rate (mGFR) Technology in Congestive Heart Failure (CHF) patients.

- Safety will be assessed by determination of the absolute and relative frequencies of AEs and SAEs related to Visible fluorescent injectate (VFI).
- Function of the FAST PV measurement will be assessed by determining the plasma stability of the FD003 high molecular weight marker over the 15, 30, and 60 minute blood draws and applying the following criteria:
  - The FAST PV measurement is considered as stable, if the mean plasma concentration of FD003 at 30 minutes is not more than 10% lower than the mean plasma concentration at 15 minutes AND if the mean plasma concentration at 60 minutes is not more than 10% lower than the mean plasma concentration at 30 minutes
  - We will determine the percentage of patients which show a decline in the plasma concentration of FD003 of more than 10% from 15min to 30min and separately from 30 min to 60min. This percentage should be ideally close to 0.

Secondary objectives are the following:

- To evaluate how estimated plasma volume (ePV) and estimated total blood volume (eTBV) assessments on days 1 and 3 (by established measures as Nadler's formula (eTBV), Kaplan-Hakim formula (ePV), Strauss formula (ePV Change)) predict measured PV (mPV; as assessed by FAST methodology) and measured TBV (mTBV; calculated from mPV and measured hematocrit) at these time points.
- To evaluate how a clinical evaluation (including a reasonable subset of the variables age, gender, BMI, hematocrit, edema grade, presence of pulmonary rales, presence of jugular venous congestion, arterial blood pressure, New York Heart Association (NYHA) stage, respiratory rate) on days 1 and 3 predicts mPV and mTBV at these time points.
- To evaluate whether estimated Glomerular Filtration Rate (eGFR) (calculation by the Chronic Kidney Disease Epidemiology Collaboration (CKD-EPI) formula, sMDRD, Cystatin C formula, and Creatinine-Cystatin C formula) on days 1 and 3 provides an accurate estimate of measured GFR (mGFR; assessed by FAST methodology) in heart failure patients undergoing active fluid management.
- To evaluate whether patients with a low mGFR/eGFR ratio on days 1 and 3 are at higher risk of developing acute kidney injury (AKI) within the following 48-72 hours.

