### 4.3 Secondary variables

#### 4.3.1 Efficacy

- Estimated PV (by Kaplan-Hakim's formula, see chapter 7.2) and measured PV (assessed by FAST methodology) on days 1 and 3
- Estimated TBV (by Nadler's formula, see chapter 7.2) and measured TBV (mTBV: calculated from mPV and measured hematocrit, see chapter 7.2) on days 1 and 3
- Estimated GFR (CKD-EPI formula, sMDRD, Cystatin C formula, and Creatinine-Cystatin C formula, see chapter 7.2) and measured GFR (assessed by FAST methodology) on days 1 and 3 in heart failure patients undergoing active fluid management
- Development of AKI within 72 hours after day 1 and 48 hours after day 3 respectively
- Current level and level within last 24 hours of well-being, dyspnea, dizziness, nausea reported on day 1 and day 3
- Subjectively reported symptoms (PGA, dyspnea, dizziness, nausea) determined using patient symptom assessment sheets within the following 24 and 48 hours on day 1 and following 24 and 48 hours on day 3
- Low-output complications within the next 24 and 48 hours (e. g. subjectively reported dizziness/nausea, PGA, hypotension (Systolic <100, diastolic <60mmHg), need for iv-fluid therapy) at day 1 and within the next 24 and 48 hours at day 3
- Risk of being refractory to diuretic therapy (e. g. require dosage increases of furosemide/torsemide, require ultrafiltration/RRT within the next 24-48 hours, fail to improve subjectively in PGA and dyspnea scales) within 24 and 48 hours on day 1 and day 3

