## 7.2 Derived Parameters

The following formulas will be used for determination of estimated and measured TBV, ideal TBV, estimated and measured total blood volume status (eTBVS and mTBVS), ePV, estimated PV change, ideal PV, estimated and measured plasma volume status (ePVS and mPVS), and eGFR on day 1 and day 3:

Nadler formula for eTBV (Sharma & Sharma, 2020):

- Men:  $eTBV [L] = (0.3669 \times \text{Height [m]}^3) + (0.03219 \times \text{Weight [kg]}) + 0.6041$
- Women:  $eTBV [L] = (0.3561 \times \text{Height [m]}^3) + (0.03308 \times \text{Weight [kg]}) + 0.1833$

mTBV will be calculated as follows:

- $mTBV [mL] = mPV [mL] / (1 - \text{hematocrit [\%]} / 100)$

Lemmens-Bernstein-Brodsky formula for ideal TBV (iTBV) (Lemmens, Bernstein, & Brodsky, 2006):

- $iTBV [mL/kg] = 70 / [\text{sqrt}(\text{body mass index}/22)]$  – the lowest body weight during the days 1 to 5 will be used for calculation of BMI
- $iTBV [mL] = iTBV [ml/kg] \times \text{weight [kg]}$  – the lowest body weight during the days 1 to 5 will be used for calculation

Estimated and measured total blood volume status:

- $eTBVS [\%] = \text{Percentage change from iTBV: } (eTBV - iTBV) / iTBV$
- $mTBVS [\%] = \text{Percentage change from iTBV: } (mTBV - iTBV) / iTBV$

Kaplan-Hakim Formula for ePV (Ling et al., 2015):

- Men:  $ePV [mL] = (1 - \text{hematocrit [\%]}) \times [1530 + (41 \times \text{weight [kg]})]$
- Women:  $ePV [mL] = (1 - \text{hematocrit [\%]}) \times [864 + (47.9 \times \text{weight [kg]})]$

Strauss formula for plasma volume change (Strauss, Davis, Rosenbaum, & Rossmeis, 1951):

- $PV\_2/PV\_1 \times 100 [\%] = \text{hemoglobin\_1 [g/dL]} / \text{hemoglobin\_2 [g/dL]} \times (1 - \text{hematocrit\_2 [\%]}) / (1 - \text{hematocrit\_1 [\%]}) \times 100$

Plasma volume change will also be calculated via the ratios of ePV by the Kaplan-Hakim-Formula

Harrison formula for ideal PV (iPV) (from Ling 2015):

- Men: iPV [mL] = 39 [mL/kg] × weight [kg] – the lowest body weight during the days 1 to 5 will be used for calculation
- Women: iPV [mL] = 40 [mL/kg] × weight [kg] – the lowest body weight during the days 1 to 5 will be used for calculation

Estimated and measured plasma volume status (ePVS and mPVS):

- ePVS [%] = Percentage change from iPV: (ePV - iPV)/iPV
- mPVS [%] = Percentage change from iPV: (mPV - iPV)/iPV

The eGFR will be calculated using CKD-EPI formula (Levey et al., 2009):

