- $$\text{eGFR [mL/min/1.73 m}^2\text{]} = 141 \times \min(\text{serum creatinine [mg/dL]/}\kappa, 1)^\alpha \times \max(\text{serum creatinine [mg/dL]/}\kappa, 1)^{-1.209} \times 0.993^{\text{age [years]}} \times 1.018 \text{ [if female]} \times 1.159 \text{ [if Black]}$$
- $\kappa = 0.7$  (females) or  $0.9$  (males)
- $\alpha = -0.329$  (females) or  $-0.411$  (males)

The eGFR will also be calculated by the CKD-EPI cystatin C formula (Inker et al., 2012):

- $$\text{eGFR [mL/min/1.73 m}^2\text{]} = 133 \times \min(\text{cystatin C [mg/L]/}0.8, 1)^{-0.499} \times \max(\text{cystatin C [mg/L]/}0.8, 1)^{-1.328} \times 0.996^{\text{Age [years]}} \times 0.932 \text{ [if female]}$$

The eGFR will additionally be calculated by the CKD-EPI creatinine-cystatin C formula (Inker et al., 2012):

- $$\text{eGFR [mL/min/1.73 m}^2\text{]} = 135 \times \min(\text{serum creatinine [mg/dL]/}\kappa, 1)^\alpha \times \max(\text{serum creatinine [mg/dL]/}\kappa, 1)^{-0.601} \times \min(\text{cystatin C [mg/L]/}0.8, 1)^{-0.375} \times \max(\text{cystatin C [mg/L]/}0.8, 1)^{-0.711} \times 0.995^{\text{Age [years]}} \times 0.969 \text{ [if female]} \times 1.08 \text{ [if black]}$$
- $\kappa = 0.7$  (females) or  $0.9$  (males)
- $\alpha = -0.248$  (females) or  $-0.207$  (males)

The eGRF will further be calculated by sMDRD (Levey et al., 2007):

- $$\text{eGFR [mL/min/1.73 m}^2\text{]} = 175 \times (\text{serum creatinine [mg/dL]})^{-1.154} \times (\text{age [years]})^{-0.203} \times 0.742 \text{ [if female]} \times 1.212 \text{ [if black]}$$

The following dose equivalents for Furosemid i.v. will be used:

- 20 mg Furosemid i.v. = 40 mg Furosemid p.o.
- 20 mg Furosemid i.v. = 20 mg Torasemid p.o.

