To evaluate whether eGFR calculation by the CKD-EPI formula and sMDRD formula on days 1 and 3 provides an accurate estimate of measured GFR (mGFR; assessed by FAST methodology) in heart failure patients undergoing active fluid management, linear regression models with the measured value at a given day as dependent variable and the estimated version as independent variable will be generated. The models will be adjusted for mPV and mPVS. Further, Bland-Altman plots will be generated comparing the estimated and measured parameters separately for day 1 and day 3. The defined limits of agreements are  $\pm 6\text{ml/min}$ . Diagnostic accuracy including frequencies of values between 15% and 30% of the measured value will be determined as mentioned before.

To evaluate whether patients with a low mGFR/eGFR ratio on days 1 and 3 are at higher risk of developing AKI within the following 72 (day 1) and 48 (day 3) hours, logistic regression models with the AKI status as dependent variable and mGFR/eGFR ratio as independent variables will be generated. The models will be adjusted for mPVS, mTBVS. Three different versions of the mGFR/eGRF ratio will be evaluated: ratio  $< 1$ ; ratio  $<$  first quartile; ratio as continuous parameter.

To evaluate whether ranges of mPVS (low mPVS ( $< -10\%$ ), normal mPVS ( $-10$  to  $+10\%$ ), high mPVS ( $> +10\%$ )) and/or mTBVS (low mTBVS ( $< -10\%$ ), normal mTBVS ( $-10$  to  $+10\%$ ), high mTBVS ( $> +10\%$ )) on days 1 and 3 are associated with subjectively reported symptoms (current PGA  $> 15$ , current dyspnea  $> 15$ , current dizziness  $> 15$ , current nausea  $> 15$ ) determined using patient symptom assessment sheets within the following 24-48 hours, a logistic regression

---

model with occurrence of symptoms (PGA, dyspnea, dizziness, nausea) as dependent variable and the categorized measured value (mPVS, mTBVS) as independent variables will be generated. The models will be adjusted for mean arterial pressure.

To evaluate whether patients with low mPVS ( $< -10\%$ ) or low mTBVS ( $< -10\%$ ) on day 1 or on day 3 are at risk of developing low-output complications within the next 24-48 hours (subjectively reported dizziness  $> 15$ , nausea  $> 15$ , PGA  $< 25$ , hypotension (Systolic  $< 100$ , diastolic  $< 60$  mmHg), need for iv-fluid therapy), logistic regression models using mPVS and mTBVS as independent variables will be used.

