To evaluate whether patients with a high mPVS ( $> +10\%$ ) or a high mTBVS ( $> +10\%$ ) on day 1 and/or day 3 are at risk of being refractory to diuretic therapy (defined as any dosage increases of furosemide i.v. dose equivalent, adding thiazide after day 1, require ultrafiltration/RRT within the next 24-48 hours, fail to improve subjectively in PGA and dyspnea scales, fail of mean weight loss during the study period Day 1-Day 5 of at least 0,5 kg/d) logistic regression models using mPV and mTBV as independent variables will be used.

To evaluate whether the changes of ePV (using relative and absolute change as well as the Strauss' formula) and eTBV (using relative and absolute change) from day 1 to day 3 adequately reflects the changes of mPV and mTBV Bland-Altman plots will be generated. These plots will be analysed exploratory, since no appropriate values for limits of agreements are available. The amount of values within 10% and within 30% of the measured values will also be determined. In addition, the diagnostic test accuracy including 95% confidence interval as proposed by Obuchowski will be calculated.

To evaluate whether the change of mPV and mTBV and changes of mPVS and mTBVS from day 1 to day 3 as well as the mPVS and mTBVS on Day 1 and Day 3 is predictive of the remaining length of stay at the given day (i.e. remaining length of stay starting with day 1 or with day 3), dialysis/ultrafiltration requirement, or rehospitalization within 30 days, or mortality, linear (remaining length of stay), logistic (dialysis/ultrafiltration, rehospitalization within 30 days) or Cox-regression models (mortality) will be utilized using changes of mPV and mTBV from day 1 to day 3 (first model), changes of mPVS and mTBVS from day 1 to day 3 (second model), and mPVS and mTBVS at day 1 (third model) and day 3 (fourth model) as independent variables.

To evaluate whether the percentage changes of mGFR from day 1 to day 3 ( $< 0$  vs.  $\geq 0$ ; continuous) predicts the percentage changes of eGFR from day 2 to day 4 (CKD-EPI formula only;  $< 0$  vs.  $\geq 0$ ; continuous), a logistic as well as a linear regression model will be used.

The same will be done to investigate the changes in eGFR from day 1 to day 3 (all formulas) as the dependent variable. Further, exploratory Bland-Altman plots without predefined limits of agreement will be created.

To evaluate whether patients with a high PVS or TBVS on Day 1 ( $> +10\%$ ) and a decreasing PVS

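### SAP 1.1 asks whether four eGFR formulas estimate mGFR accurately on days 1 and 3, but the accuracy analysis in SAP 7.7.1 names only two of them

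*SAP*

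**What the plan says.** The objective in SAP 1.1 covers eGFR by "calculation by the Chronic Kidney Disease Epidemiology Collaboration (CKD-EPI) formula, sMDRD, Cystatin C formula, and Creatinine-Cystatin C formula) on days 1 and 3" and asks whether it estimates mGFR accurately. SAP 4.3.1 carries the same four into the list of secondary variables: "Estimated GFR (CKD-EPI formula, sMDRD, Cystatin C formula, and Creatinine-Cystatin C formula, see chapter 7.2) and measured GFR". SAP 7.2 provides an equation for each, for use on day 1 and day 3.

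The corresponding analysis in SAP 7.7.1 begins "To evaluate whether eGFR calculation by the CKD-EPI formula and sMDRD formula on days 1 and 3 provides an accurate estimate of measured GFR". It then specifies four things for each day: a regression of mGFR on eGFR, a Bland-Altman plot with limits of ±6 ml/min, the frequency of values within 15% and 30% of the measured value, and the diagnostic accuracy index. Neither cystatin C formula is mentioned in that paragraph.

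Later in 7.7.1, a separate set of models takes "changes in eGFR from day 1 to day 3 (all formulas) as the dependent variable". The version history describes the change made at version 1.0 as "Inclusion of Cystatin C formulas for estimation of GFR". SAP section 8 adds that cystatin C was recorded during the study and will be used in the estimation formulas.

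**The concern.** An objective needs an analysis that answers it. Here the question covers four formulas and the analysis covers two, both of which rest on serum creatinine. A statistician who follows 7.7.1 as written would produce no per-day accuracy result for either formula that uses cystatin C. The report could then describe how creatinine-based eGFR compares with mGFR, but would have no planned result on whether any disagreement also appears when cystatin C is used. If the missing comparisons were added after results had been seen, they would be post hoc, although the SAP posed the question in advance.

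**Working it through.** No sample size, power or alpha figure is involved, and the plan gives no figure to reproduce. The check is a comparison of the SAP's own sections, followed by a count.

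| Place in the SAP | Creatinine CKD-EPI | sMDRD | Cystatin C | Creatinine-cystatin C |
|---|---|---|---|---|
| 1.1, objective | yes | yes | yes | yes |
| 4.3.1, variables | yes | yes | yes | yes |
| 7.2, equations | yes | yes | yes | yes |
| 7.7.1, accuracy on each day | yes | yes | not named | not named |
| 7.7.1, eGFR change from day 2 to day 4 | yes | no | no | no |
| 7.7.1, eGFR change from day 1 to day 3 | yes | yes | yes | yes |

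**Count.** The objective implies 4 formulas × 2 days = 8 comparisons with mGFR. The accuracy paragraph specifies 2 × 2 = 4. That leaves 8 − 4 = 4 without a specified analysis, which is 4/8, or half.

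**Could the CKD-EPI label include the cystatin C equations?** SAP 7.2 does attach the CKD-EPI name to them, for example "The eGFR will also be calculated by the CKD-EPI cystatin C formula". But the unqualified name is introduced with "The eGFR will be calculated using CKD-EPI formula", and the equation that follows uses serum creatinine and no cystatin C. More decisively, 1.1 and 4.3.1 list the CKD-EPI formula as one item and the two cystatin C formulas as further items. If the label covered all three, those lists would count the same formulas twice.

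**Do the change models fill the gap?** They relate the percentage change in mGFR to the percentage change in eGFR. Suppose a formula returns k × mGFR on both days. Its percentage change is (k·mGFR3 − k·mGFR1)/(k·mGFR1) = (mGFR3 − mGFR1)/mGFR1, which is identical to that of mGFR whatever the value of k. With k = 0.7, a formula reading 30% too low on both days would track change perfectly. A proportional bias of this kind is therefore invisible to these models, whereas the per-day accuracy analysis is designed to show it. The Bland-Altman plots attached to the change analysis also have no predefined limits.

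**Does SAP section 8 fill the gap?** It shows an intention to use cystatin C, but assigns it to no accuracy analysis. It also does not announce that the cystatin C formulas are to be restricted to change.

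**The case against.** The strongest reply is that the intent is already clear. Sections 1.1, 4.3.1, 7.2 and 8 all point to using cystatin C, so one unrevised sentence in 7.7.1 would not stop a sensible statistician from running all four formulas. Moreover, the protocol (section 4.2 and section 14) asks only about CKD-EPI, so the protocol's own question is fully analysed, with sMDRD added. All analyses are declared descriptive and hypothesis-generating.

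Most of this stands. It limits the weight of the point and supports reading the omission as an oversight, but it does not remove it. Section 7.7.1 is where the analysis is specified, and it disagrees with the SAP's stated objective.

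Several stronger readings are tempting and should not be adopted:

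- A reader might infer that the sponsor deliberately excluded cystatin C from the accuracy question. The version history and section 8 point the other way.
- A reader might infer that cystatin C enters nothing except the change models. The documents support only that it is explicitly included there; the mGFR/eGFR ratio analysis names no formula, so its use in that analysis is not ruled out.
- A reader might take the contrast in the change paragraph, between using CKD-EPI alone and using all formulas, as proof of what the label means. It is not, because the contrast would also hold if sMDRD were the only formula left out. The separate listing in 1.1 and 4.3.1 is the better evidence.
- A reader might want to express the gap as a number of ml/min between formulas. The documents give no cystatin C distribution, so any such figure would depend on the value assumed. The ±6 ml/min limits apply to eGFR against mGFR, not to one eGFR formula against another.

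**Conclusion.** The point holds as an inconsistency within the SAP. Half of the formula-by-day comparisons implied by the objective in 1.1 (4 of 8) have no specified accuracy analysis, and neither the change models nor section 8 supplies one. Section 4.3.1 only lists variables; the accuracy question itself is posed in 1.1.

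The consequence is confined to a secondary, descriptive objective that the SAP extended beyond the protocol. A reader might infer that the trial cannot answer its protocol question on eGFR, or that the primary assessment is weakened. Neither follows: CKD-EPI is analysed on both days, and the primary assessment of safety and FD003 stability does not use eGFR.

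The conclusion assumes that the unqualified CKD-EPI name means the creatinine equation, as 1.1, 4.3.1 and 7.2 indicate. It also assumes that cystatin C is available on days 1 and 3, which 7.2 presupposes; the documents do not say in how many patients. It remains worth correcting because the data are already recorded and the change is nearly free.

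**What to change.** In the accuracy paragraph of SAP 7.7.1, replace the two named formulas with all four defined in 7.2, so that the regression, Bland-Altman analysis, 15% and 30% frequencies and diagnostic accuracy are produced for each formula on each day.

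Keep each formula's analysis on all patients who have the markers it needs. This way the protocol's CKD-EPI analysis loses nobody for lack of cystatin C. Add a supplementary comparison of the formulas restricted to patients with both creatinine and cystatin C on that day. It is useful because SAP 5.1 replaces missing day 1 and day 3 creatinine but gives no such rule for cystatin C, so the formulas may otherwise be assessed on different patients.

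If the restriction to two formulas was intended, the alternative is to say so in 7.7.1 and bring 1.1 and 4.3.1 into line with it.

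The cost is a short edit before the analysis, four more descriptive comparisons and the supplementary table. According to section 8, cystatin C was recorded, so no new data collection is needed.

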## 8 Changes from the protocol

In general, no variable selection will be done in the regression models due to limited sample size. Rather clinical expertise regarding the most important explanatory variables will be used to determine a fixed, hierarchical set of possible covariates.

The mPVS and mTBVS are used to determine patients with low, normal or high PV and TBV and thus, the status will be defined based on established estimation formulas for ideal PV and TBV incorporating weight and/or height.

The analysis of the time course of estimated and measured PV and TBV via t-tests was replaced by Bland-Altman-analyses since these analysis better reflects the underlying question of clinically equivalent measurements. Further, the curve characteristics (e.g. times when maximal and minimal volumes are reached and the areas under the curve) based on only few time points were deemed to be of minor meaningfulness.

Haemoglobin for estimating plasma volume changes by Strauss formula and cystatin C values to estimate Glomerular Filtration Rate were also recorded during the study and will also be utilized for the analysis in the respective estimation formulas.

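### The AKI models leave open both the eGFR in the mGFR/eGFR ratio and AKI's reference creatinine; if both use the dosing-day creatinine, predictor and outcome are coupled

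*SAP*

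**What the plan says.** The outcome is listed in SAP 4.3.1 as "Development of AKI within 72 hours after day 1 and 48 hours after day 3 respectively". SAP 7.7.1 specifies "logistic regression models with the AKI status as dependent variable and mGFR/eGFR ratio as independent variables will be generated", one model for each dosing day. On the predictor it says "Three different versions of the mGFR/eGRF ratio will be evaluated": below 1, below the first quartile, and continuous. On covariates it says "The models will be adjusted for mPVS, mTBVS".

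SAP 7.2 starts with the creatinine formula, "The eGFR will be calculated using CKD-EPI formula", and then adds "The eGFR will also be calculated by the CKD-EPI cystatin C formula", a combined creatinine-cystatin C formula and sMDRD. Three of the four contain serum creatinine. SAP 8 states that "cystatin C values to estimate Glomerular Filtration Rate were also recorded during the study". The protocol's own objectives (4.2 and 14) name CKD-EPI only.

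Two things are not stated. The AKI paragraph of SAP 7.7.1 does not say which eGFR enters the ratio. Neither document gives an AKI criterion or reference creatinine for this trial; AKI staging systems appear only in the account of an earlier study (protocol 3.1.3.3). Several creatinines could serve as reference: a pre-study nadir and an admission value (protocol Table 8), and the Day 1 to Day 5 values (protocol Tables 7 and 8).

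**The concern.** A creatinine-based eGFR for Day 1 or Day 3 is computed from that day's creatinine. If AKI is then judged as a rise from the same value, a single error enters both sides of the model. A creatinine that reads low by chance makes eGFR too high and the ratio too low, and its return to the usual level looks like a rise. Both effects push towards the association the objective asks about, that a low ratio precedes AKI, even if mGFR says nothing about future AKI.

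The three versions of the ratio do not check one another, because all have the same denominator. The SAP states that its aim is to generate hypotheses for phase III, so a built-in association could be carried forward as a finding.

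**Working it through.** The plan gives no AKI rate, effect size or power for this analysis, so there is no figure to reproduce. The check has three steps.

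**1. Do the adjusters contain creatinine?** By SAP 7.2, mPVS is built from mPV and body weight, and mTBVS from mPV, hematocrit, weight and BMI. Neither contains creatinine, so neither can absorb an error in it.

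**2. Algebra with the SAP's exponents.** Above kappa, CKD-EPI creatinine eGFR is proportional to creatinine^-1.209. For a creatinine that is 10% low by chance:

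- eGFR is multiplied by 0.9^-1.209 = 1.136 (13.6% too high), and the ratio by 0.9^1.209 = 0.880 (12.0% too low).
- With sMDRD (exponent -1.154), the ratio is multiplied by 0.9^1.154 = 0.886 (11.4% too low).
- With the combined formula (creatinine exponent -0.601), the ratio is multiplied by 0.9^0.601 = 0.939 (6.1% too low).
- Return to the true value appears as a rise of 0.10 × 1.5 = 0.15, 0.10 × 2.0 = 0.20 or 0.10 × 3.0 = 0.30 mg/dL at true creatinines of 1.5, 2.0 and 3.0 mg/dL.

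**3. Simulation with no true association.** These inputs are assumptions, not in the documents: median creatinine 1.5 mg/dL, mGFR error 12%, AKI as a rise of at least 0.3 mg/dL or 1.5-fold, real creatinine change with an SD of about 15-20%, and a true between-patient SD of the ratio of 0-25%. Odds ratios compare the lowest quartile of the ratio with the rest.

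| AKI rule and denominator | Creatinine error | Null odds ratio |
|---|---|---|
| Rise from dosing-day creatinine; creatinine eGFR | 3% | about 1.1-1.2 |
| same | 5% | about 1.2-1.5 |
| same | 8% | about 1.4-2.2 |
| AKI new against the pre-study nadir; creatinine eGFR | range of errors | about 1.05-1.45 |
| Any AKI against the nadir; creatinine eGFR | range of errors | about 1.00-1.05 |
| Rise from dosing-day creatinine; denominator error independent of it | range of errors | about 1.00-1.05 |

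The nadir row with new AKI is not null because the dosing-day creatinine then decides who is AKI-free at the start. A chance-low value lets a patient in and lowers the ratio at the same time.

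The size depends on the inputs. More true spread in the ratio, or more real creatinine change, dilutes it. With no real change, no true spread and mGFR error 15%, the dosing-day rule gives 2.30 at 5% error and 2.90 at 8%.

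For trials of 50 patients, I took mGFR error 15%, real change 15%, no true spread, and no mPVS or mTBVS adjustment. The continuous ratio then reached p<0.05 in 6.5%, 18% and 33% of null trials at 5%, 8% and 10% creatinine error. With AKI measured from a separate earlier creatinine, this happened in 3.5-4.5% of trials.

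**The case against.** The strongest reply is that the coupling is not in the text. A reader might infer that the plan puts one creatinine on both sides, so that any association found would be an artefact. The documents do not support that. They give no reference value, and they record a pre-study nadir under the name of baseline creatinine, which SAP 4.1 lists separately from the Day 1 value. It is at least as natural a reference, and if any AKI against it counts, the artefact all but vanishes. Nor does the SAP exclude cystatin C here: it lists four eGFR formulas, and where it wants CKD-EPI alone, as in the Day 2 to Day 4 eGFR analysis, it says so. This stands, and the point is therefore conditional. It does not close the point, because a text that leaves both choices open permits the coupled analysis. The wording about developing AKI after the dosing day also suggests new onset, which brings the dosing-day creatinine back in, as reference or to define who is at risk.

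Second, the size rests on assumed errors and is modest at 3-5%. This also stands.

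Third, a creatinine that has not yet caught up with a falling GFR, and then rises, is the very signal under study. Dilution is related to plasma volume, which mPVS and mTBVS may partly capture. Both are fair, but neither covers assay error or random day-to-day variation.

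Fourth, all analyses are declared descriptive. That limits the harm but does not remove a directional bias from a hypothesis-generating result.

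**Conclusion.** The concern holds as a conditional one. The SAP leaves the eGFR in the ratio and AKI's reference creatinine undefined. If a creatinine-based eGFR meets an AKI rule that uses the dosing-day creatinine, the model is biased towards a low ratio predicting AKI, and nothing planned corrects it.

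Under the stated assumptions the bias is small at 3% creatinine error, moderate at 5% and substantial at 8%. It is weaker if AKI must be new against the nadir, and close to nil if any AKI against the nadir counts or the denominator's error is independent of that creatinine. The creatinine error, the mGFR error, the AKI rule, the real creatinine change and the spread of the true ratio are all assumed. The primary analysis is not affected.

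**What to change.** In SAP 7.7.1, before analysis:

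1. Use mGFR divided by CKD-EPI cystatin C eGFR (SAP 7.2) as the main ratio in the AKI models. Show the CKD-EPI creatinine ratio, the protocol's formula, beside it with a note on the coupling.
2. State the AKI criterion, which recorded creatinine is its reference, and whether AKI must be new. Do not take the reference and the ratio's denominator from the same sample.
3. In these models, do not apply the SAP 5.1 rule that fills a missing Day 3 creatinine from Day 4. Day 4 lies inside the 48-hour outcome window, so the rule puts outcome data into the predictor.

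Splitting the study and routine creatinines of one day between ratio and AKI reference is not a sufficient substitute, because they share day-to-day and dilution error. If 50-75% of the error variance is of that kind, the null odds ratio at 8% error is still 1.24-1.45.

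The cost is SAP wording. Patients without cystatin C on Day 1 or Day 3 drop out of the main ratio. The protocol's laboratory tables do not list cystatin C and SAP 8 gives no time points, so its availability on both days should be confirmed first. That cystatin C is unaffected by dilution is itself an assumption, to be stated with the result.
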